2.3. Treatment and intervention plans

(1) Test chemicals/test equipment

Radiation therapy X-rays or electron beams generated by radiation therapy equipment installed in the Department of Radiation Therapy at Fukushima Medical University

Hospital and the Department of Radiation Oncology at Kanagawa Cancer Center.

Nivolumab (Anti-PD-1 Ab) Ono Pharmaceutical Industries Ltd/Bristol-Myers Squibb Co.

Opdivo intravenous infusion 20 mg, 100mg

(2) Dosage/applications

Radiotherapy

Exposure 22.5 Gy/5 times/5 days

Irradiation range

In accordance with the usual treatment methods used in symptomatic and palliative treatment, only the tumor is targeted and the irradiated area has a margin that takes into account the physical uncertainties assumed at each irradiated site (i.e. the clinical and prophylactic irradiation area is not considered).

Basis for setting

Prognosis and early initiation of nivolumab therapy are priorities, and the main target lesions were assumed to be liver metastases, lymph node metastases, local (surgical) recurrent lesions and bone metastases. Therefore, the radiotherapy period was kept short and the irradiation dose was set at 22.5 Gy/5 times/5 days, which is below the tolerable dose at each site and close to the tolerable dose in the brain and spinal cord.

Selection of irradiated tumors

If symptoms such as pain or paralysis are present, the lesion thought to be the main cause of symptoms should be selected; if asymptomatic, the largest lesion (or the second largest if radiotherapy of the largest lesion is difficult) should be selected. Tumors larger than 2 cm should be selected, taking into account the possibility that tumors that are too small may not cause an adequate biological response (induction of anti-tumor immunity).

Irradiation day interval

Radiotherapy is performed on consecutive Department of Radiation Therapy working days (weekdays and consecutive days). This does not apply during the end of the year and New Year holidays, national holidays and other holidays.). The day that radiotherapy is started is Day 1. If radiotherapy is not completed by Day 14, the patient is considered to have dropped out.

Irradiation implementation conditions

On each irradiation day, ensure that all of the following conditions are met before the day's irradiation

- 1) Body temperature: < 38.5°C (axilla)
- 2) Confirmation by the attending doctor that there are no problems with radiotherapy.

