2.6. Evaluation items

The primary endpoint of this clinical trial is the disease control rate of non-irradiated target lesions, in order to explore the efficacy (additive effect) of radiotherapy to immunotherapy with nivolumab, which is already established as third-line chemotherapy in unresectable advanced or recurrent gastric cancer. Secondary endpoints will also include 1) median survival time (MST) and 2) safety (grade and frequency of adverse events), 3) local control rate (disease control rate of irradiated target lesions), and 4) immunological parameters.

(1) Primary endpoint

Disease control rate

The rate of patients with a best overall response of stable disease (SD) or better confirmed by 180 days, starting from the start date of radiotherapy (Day 1). CT (MRI is also acceptable) and whole-body PET-CT will be used to determine overall response such as complete response (CR), partial response (PR), SD, progressive disease (PD) at each imaging time according to the RECIST Guidelines Version 1.1. If imaging is not available, the patient is considered deficient (NE). CR or PR as the best overall response is defined as two or more consecutive CRs or PRs. If the best overall response does not meet the criteria for CR or PR, and the patient has no PD on the 6th dose of nivolumab and Day 120, the best overall response is considered to be SD. For evaluation, target lesions other than those treated with local radiotherapy are considered as target lesions. If the lesions cannot be evaluated based on the above criteria, they will not be included in the analysis for best overall response.

(2) Secondary endpoint

1) Median survival time (MST)

Overall survival is defined as the period from the start date of radiotherapy until the date of death from any cause. In surviving cases, the last date of confirmation of survival is the date of termination (survival confirmed by telephone contact is acceptable, but confirmation of survival should be recorded in the medical record). Untraceable cases are terminated on the last date of confirmed survival before the loss of follow-up. At the end of the study period, all enrolled cases will be confirmed alive.

2) Safety (grade and frequency of adverse events)

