2.10. Statistical analysis

(1) Statistical analysis of the evaluation

The composition of the population to be analyzed shall be as follows:

- 1) All enrolled cases: the population of enrolled patients, excluding duplicate enrollments and incorrect enrollments.
- 2) All eligible cases: the population excluding ineligible cases (posterior ineligibility, ineligibility at enrollment, offending enrollment) from all enrolled cases.
- 3) Largest analyzed population (FAS): all eligible cases for whom treatment was administered.

(2) Method of analysis

Primary endpoints

- 1) Disease control rate

For FAS cases, summarize the responses of non-irradiated target lesions in a contingency table, and calculate the cumulative disease control rate and the Clopper & Pearson two-side 90% confidence interval. The disease control rate was defined as the total number of patients with CR/PR/SD divided by the number of eligible patients.

Secondary endpoint

- 1) MST

For FAS cases, estimate the MST using the Kaplan-Meier method, along with a two-sided 95% confidence interval using the Brookmeyer-Crowley method.

- 2) Safety

For all enrolled cases, data regarding AEs and toxicities were tabulated, and the Clopper & Pearson two-sided 95% CI was calculated.

- 3) Local control rate

For FAS cases, summarize the responses of irradiated target lesions in a contingency table, and calculate the cumulative disease control rate and the Clopper & Pearson two-side 90% confidence interval. The disease control rate was defined as the total number of patients with CR/PR/SD divided by the number of eligible patients.

- 4) Immunological parameters

Analyzes are performed at Fukushima Medical University Hospital, Kanagawa Cancer Centre,

and by outsourced testing, as appropriate.

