3.1 Case handling

The principal investigator decides on the handling of cases before the data are fixed, following a review of eligibility and non-compliance with the Study Protocol at the case review meeting.

- 1) All enrolled cases: the population of enrolled patients excluding duplicate enrollments and incorrect enrollments.
- 2) All eligible cases: the population excluding ineligible cases (posterior ineligibility, ineligibility at enrollment, offending enrollment) from all enrolled cases.
- 3) Largest analyzed population (FAS): all eligible patients for whom treatment was administered.
- 4) Safety analysis population: all enrolled cases, those for whom treatment was administered.

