3.2 Analysis population

Efficacy is examined in the FAS and safety is examined in the safety analysis population.

4. Examination of test reliability

1) Purpose

Describe the occurrence of major registration violations, discontinuations, drop-outs, etc. in all enrolled cases, and specify the population to be analyzed.

2) Analysis population

All enrolled cases.

3) Analysis items

- (1) Number of cases belonging to the analyzed population.
- (2) Early discontinued or not.
- (3) Any deviations from the Study Protocol.

4) Method of analysis

- (1) Number of cases in the enrolled, eligible, and largest analyzed cohort are tabulated.
- (2) Cases of early discontinuation are tabulated according to reason and institution.
- (3) Cases of deviation from the Study Protocol are tabulated according to reason and institution.
- (4) A list of cases of treatment failure, early discontinuation, and deviations from the Study Protocol is prepared.

5. Comparability considerations

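### Protocol 2.6 can be read as dropping non-evaluable patients from the disease control rate, against the 2.10 formula; 2.10 also mixes FAS and eligible patients, and the SAP settles neither point

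*Protocol*

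**What the plan says.** Protocol 2.6 defines the primary endpoint as the proportion of patients whose best overall response in the non-irradiated target lesions is SD or better by Day 180. A patient without imaging is labelled NE. SD requires no PD at the sixth nivolumab dose and at Day 120. The paragraph ends: "If the lesions cannot be evaluated based on the above criteria, they will not be included in the analysis for best overall response". The same sentence closes the definition of the local control rate.

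Protocol 2.10 opens its primary analysis with "For FAS cases, summarize the responses of non-irradiated target lesions in a contingency table" and then gives the formula: "The disease control rate was defined as the total number of patients with CR/PR/SD divided by the number of eligible patients". The local control rate uses the same formula.

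SAP 3.1 defines the analysis set as "Largest analyzed population (FAS): all eligible patients for whom treatment was administered", and SAP 3.2 adds: "Efficacy is examined in the FAS and safety is examined in the safety analysis population". SAP 6.1 and 6.2.2 ask for a contingency table, the rate and its two-sided 90% Clopper-Pearson interval. They give no denominator and no rule for NE. SAP 6.5 plans no missing-data sensitivity analysis.

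**The concern.** Best overall response is assigned per patient, and the DCR is built from it. If the closing sentence of 2.6 is applied to patients, an NE patient leaves both numerator and denominator. Under the 2.10 formula the same patient stays in the denominator and counts as not controlled. Two analysts could therefore report different primary results from the same data, each with a section of the protocol in support.

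Patients without a usable later scan are foreseeable. Protocol 2.3 says: "If radiotherapy is not completed by Day 14, the patient is considered to have dropped out". SAP 5.2 nevertheless counts patients with unfinished radiotherapy within the FAS. The examination at discontinuation is done only if circumstances allow (Protocol 2.5), and Protocol 2.7 anticipates patients who have died or cannot attend. Protocol 2.7 also records PD judged from imaging and clinical findings, but nothing links that judgement to best overall response.

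A second, smaller mismatch lies inside 2.10. It names the FAS as the analysis set and eligible patients as the denominator. The FAS is the treated subset of eligible patients, and SAP 4 treats them as distinct counts: "Number of cases in the enrolled, eligible, and largest analyzed cohort are tabulated".

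This is a single-arm trial whose main efficacy result is one proportion, so the denominator should not be left to interpretation.

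**Working it through.** **The plan's own figure.** Protocol 2.8 gives p0 = 0.40, an improvement of 20 points (p1 = 0.60), one-sided 5% and power 80%. By the arcsine formula, n = [(1.645 + 0.842) / (2·arcsin√0.60 − 2·arcsin√0.40)]² = (2.487 / 0.4027)² ≈ 38.1, rounded up to 39. This matches the protocol, and the denominator question does not change it.

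**The texts side by side.**

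| Reading | NE patient in the denominator? | Consistent with 2.10? |
|---|---|---|
| 2.6 applied to patients | No | No |
| 2.6 applied to lesions only | Yes, as not controlled | Yes |
| 2.10 formula | Yes, as not controlled | – |
| SAP 3.2, 6.1, 6.2.2 | FAS named; NE not addressed | Not settled |

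**Effect on the interval.** The Clopper-Pearson 90% lower limit for x of n is the 5th percentile of Beta(x, n − x + 1). The NE and untreated counts are assumed. The limit is read against the 40% in 2.8, which is an inference.

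| Case | All 40 | Reduced denominator |
|---|---|---|
| 4 NE dropped, 20 controlled | 20/40 = 50.0%, limit 36.1% | 20/36 = 55.6%, limit 40.6% |
| 4 NE dropped, 21 controlled | 21/40 = 52.5%, limit 38.5% | 21/36 = 58.3%, limit 43.3% |
| 2 NE dropped, or 2 eligible untreated, 21 controlled | 21/40 = 52.5%, limit 38.5% | 21/38 = 55.3%, limit 40.7% |
| 1 NE dropped, or 1 eligible untreated, 21 controlled | 21/40 = 52.5%, limit 38.5% | 21/39 = 53.8%, limit 39.6% |

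With all 40 in the denominator, 22 controlled patients are needed for a limit above 40% (22/40 gives 40.9%). With 4 NE dropped, only counts of 20 and 21 change side. With 2 or 3 dropped only 21 does, and with 1 none does.

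**Chance of a limit above 40% when the true all-patient DCR is 40%.** Let f be the NE share and q the share of NE patients who are failures. If NE patients are dropped, the evaluable number is Binomial(40, 1 − f), and the control rate among evaluable patients is (0.40 − f(1 − q)) / (1 − f). At f = 0.10:

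- q = 1: 0.40/0.90 = 0.444
- q = 0.8: 0.38/0.90 = 0.422
- q = 0.6: 0.36/0.90 = 0.400

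Applying the exact cut-off at each evaluable number gives the table below. With no NE the chance is 3.9%.

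| NE share | All NE fail | 80% fail | 60% fail | 50% fail |
|---|---|---|---|---|
| 5% | 6.1% | 4.6% | 3.5% | 3.0% |
| 10% | 10.5% | 6.4% | 3.6% | 2.6% |
| 15% | 17.3% | 8.7% | 3.7% | 2.3% |
| 20% | 26.7% | 11.7% | 3.8% | 1.9% |

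The break-even is q = 0.60 for every f, because the evaluable rate then equals 0.40.

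**Cost of counting NE as not controlled.** With a true DCR of 60% and 10% NE, the counted rate is 0.60 − 0.10(1 − q). The chance of at least 22 of 40 is:

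- 79.1% at 0.60 (all NE are failures)
- 70.9% at 0.58 (80% are)
- 61.5% at 0.56 (60% are)

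**The case against.** The best defence is that 2.6 speaks of lesions, not patients. The sentence directly follows the one naming non-irradiated lesions as targets. Protocol 2.4 uses the same idea: when a further lesion needs palliative radiotherapy, observation continues if other evaluable lesions remain. On that reading a lesion drops out, the patient stays, and 2.10 is the only stated denominator. The NE label may also belong to one imaging time rather than to the patient. This reading is at least as natural as the patient-level one. It removes the conflict but not the ambiguity, because the SAP is silent.

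On the second point, eligible patients in 2.10 may be shorthand for the FAS just named. A reader might infer that the SAP contradicts the protocol here. It does not: it names only the FAS and states no competing denominator.

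The plan also has safeguards. SAP 8.7 lists best overall response for every FAS patient and SAP 8.2 lists exclusions from the FAS, so either rate could be recovered afterwards. That helps a careful reader of the listings, but it does not fix the primary figure in advance.

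Finally, no document tests the interval against 40%, and 2.8 does not say whether that 40% was calculated on evaluable or all treated patients. Both objections stand. They limit what can be said about size, not the need to state the denominator.

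**Conclusion.** The ambiguity is certain and should be fixed; bias is only conditional. Read at patient level, 2.6 conflicts with 2.10 for both the DCR and the local control rate. Read at lesion level, it does not.

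A reader might infer that the plan excludes NE patients and so inflates its primary result, or that its false-positive rate rises to 10% or more. The documents do not support that. They state no decision rule and give neither an NE share nor a failure share. The calculated chance rises only if NE patients are dropped and more than 60% of them are failures. The largest figure, 26.7%, needs 20% NE with every one a failure. At 10% NE the range is from 10.5% down to no rise.

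The mix of FAS and eligible patients lies within 2.10 and has no effect if every eligible patient is treated. One untreated patient among 40 moves no count across 40%; two affect only a count of 21. The trial is described as an exploratory proof of concept, which limits the consequence but does not make an open denominator acceptable.

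**What to change.** - In both places in Protocol 2.6, limit the closing sentence expressly to lesions, or delete it.
- State one denominator in Protocol 2.10 and SAP 6.1 and 6.2.2: all FAS patients. A patient whose best overall response over all scans to Day 180 cannot be classed as CR, PR or SD under 2.6 counts as not controlled. This includes death or progression before classification is possible.
- Say that NE at one time point does not by itself make the patient NE. State how a patient without PD who misses the sixth-dose or Day 120 scan is classed.
- Replace eligible patients in 2.10 with FAS patients, and report the number of eligible untreated patients beside the rate. SAP 4 already tabulates both counts.
- The evaluable-only rate may be shown as a labelled secondary figure; SAP 6.5 would then need a matching change.

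The cost is wording only: no new data, visits or patients. There are two downsides. The rate is conservative if some NE patients were in fact controlled, as the fall from 79.1% to 70.9% or 61.5% shows. It is also slightly higher than the literal 2.10 rate if an eligible patient goes untreated (21/38 against 21/40), which is why the untreated count belongs beside it.

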The frequency of adverse events occurring from the start date of radiotherapy to the end of study will be tabulated by adverse event name and worst grade according to CTCAE ver.4.0. All adverse events are summarized without regard to causal relationships to the study treatment. A serious adverse event is defined as having occurred if at least one of the following adverse events is observed, and the frequency and proportion of serious adverse events is calculated.

- ① Death during protocol treatment or within 30 days of last protocol treatment.
- ② Death with undeniable causal relationship to protocol treatment after 31 days of last protocol treatment.
- ③ Grade 4 infection with neutropenia.
- ④ Grade 4 non-hematological toxicity (excluding adverse events in the blood/bone marrow).

3) Local control rate

The rate of patients with a best overall response of SD or better confirmed by 180 days, starting from the start date of radiotherapy (Day 1). CT (MRI is also acceptable) and whole-body PET-CT will be used to determine overall response such as complete response (CR), partial response (PR), SD, progressive disease (PD) at each imaging time according to the RECIST Guidelines Version 1.1. If imaging is not available, the patient is considered deficient (NE). CR or PR as the best overall response is defined as two or more consecutive CRs or PRs. If the best overall response does not meet the criteria for CR or PR, and the patient has no PD on the 6th dose of nivolumab and Day 120, the best overall response is considered to be SD. For evaluation, target lesions are tumors that are treated with local radiotherapy. If the lesions cannot be evaluated based on the above criteria, they will not be included in the analysis for best overall response.

4) Immunological parameters

Histological examination

- Analysis of the tumor microenvironment by immunohistochemistry.
 - * Immunohistochemistry will be performed in cases with available biopsy and/or resected surgical specimens.

Peripheral blood test

- Analysis of peripheral blood lymphocyte subset
- Measurement of cytokines in plasma
- Analysis of regulatory T cell and antigen-specific T cell function

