3.1. Inclusion criteria

Subjects who meet all of the following criteria are eligible in this study.

- 1) Patients with unresectable advanced or recurrent gastric cancer with intolerance or progression after standard treatment (primary and secondary chemotherapy).
- 2) Patients with more than one measurable lesion and with at least one lesion ≥ 2 cm as defined by the RECIST guidelines edition 1.1 on diagnostic imaging (whole-body contrast-enhanced CT or PET-CT) within 14 days before entry.
- 3) Age ≥ 20 years.
- 4) ECOG performance status (PS): 0–2.
- 5) No contraindication for nivolumab (anti-PD-1 Ab) administration.
- 6) No contraindication for radiotherapy.
- 7) The patient's most recent laboratory tests within 14 days prior to enrollment must meet the following criteria. However, if the clinical examination at the time of enrollment is not included within 7 days prior to the first dose of nivolumab, a repeat examination should be performed within 7 days prior to the first dose of the study drug to reconfirm that the most recent clinical examination prior to the first dose of nivolumab meets the criteria below. In all cases, the laboratory values must not have received a G-CSF product or blood transfusion within 14 days prior to the date of testing.

White blood cell count $\geq 3,000/\mu\text{L}$ and neutrophil count $\geq 1,500/\mu\text{L}$

Hemoglobin $\geq 9.0 \text{ g/dL}$

Platelets $\geq 100,000/\mu\text{L}$

Total bilirubin ≤ 2.0 times the institutional standard upper limit (ISUL)

AST (GOT) and ALT (GPT) ≤ 3.0 times ISUL (in case with liver metastasis, ≤ 5.0 times ISUL).

Serum creatinine ≤ 1.5 times ISUL or creatinine clearance (Ccr) estimate $\geq 60 \text{ mL/min}$.

Ccr is calculated by the Cockcroft-Gault formula:

Male Ccr = $\{(140 - \text{age}) \times \text{weight (kg)}\} / \{72 \times \text{serum creatinine level (mg/dL)}\}$

Female Ccr = $0.85 \times \{(140 - \text{age}) \times \text{weight (kg)}\} / \{72 \times \text{serum creatinine level (mg/dL)}\}$

- 8) Patients expected survival ≥ 3 months.

9) Written informed consent is obtained from the patient prior to study enrollment.

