3.2. Exclusion criteria

Subjects who meet the following criteria are not eligible to enroll in this study:

- 1) Patients with no tumor lesions that can be irradiated.
- 2) Patients with metachronous and simultaneous overlapping cancers (excluding intraepithelial cancer of the uterine cervix, fully treated basal cell carcinoma of the skin, and malignant tumors that were treated more than 5 years ago and have not recurred).
- 3) Patients with a history of severe hypersensitivity reactions to other Ab products.
- 4) Patients taking immunosuppressive drugs or corticosteroids (prednisone or prednisolone equivalent ≥ 15 mg/day).
- 5) Patients with active autoimmune diseases or a history of recurrent autoimmune diseases (patients with type-1 diabetes, hypothyroid controllable by hormone replacement therapy, and dermatosis without the need for systemic therapy are eligible).
- 6) Patients with complications or history of interstitial pneumonia or pulmonary fibrosis diagnosed by imaging studies or clinical findings.
- 7) Patients with presence of severe disease or medical condition such as severe nutritional deficiencies, transient ischemic attack within 180 days prior to enrollment, cerebral vascular attack within 180 days prior to enrollment, thrombus or thromboembolism within 180 days prior to enrollment, congestive heart failure (NYHA class III or IV), unstable angina, myocardial infarction within 12 months, severe arrhythmias requiring medication, conduction abnormalities such as AV block beyond the second degree, uncontrollable hypertension, liver cirrhosis (Child Class B or higher), mental disorders that may interfere with compliance with this study protocol, unstable diabetes, uncontrolled pericardial fluid, uncontrolled ascites, uncontrolled pleural effusions, diseases requiring anticoagulation therapy (excluding antiplatelet therapy including low-dose aspirin), and systemic infection with treatment.
- 8) Pregnant or lactating female.
- 9) Fertile female who are unwilling to use contraception.
- 10) Fertile male who are not willing to use contraception during study drug administration and for 7 months after study completion (if the partners are fertile females).
- 11) Prohibited previous treatment
Within 56 days of registration: radioactive drugs (except radiopharmaceuticals for examination or diagnostic purposes).

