6.2.2 Local control rate

1) Purpose

To explore the efficacy of protocol treatment for unresectable advanced or recurrent gastric cancer, determine the local control rate of the best overall response, which is SD or better, confirmed by Day 180.

2) Analysis items

Local control rate (disease control rate of irradiated target lesions).

3) Analysis methods

- (1) Construct a waterfall plot for the local control rate.
- (2) Summarize the responses of irradiated target lesions in a contingency table, and calculate the cumulative disease control rate and the Clopper & Pearson two-side 90% confidence interval.

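### The irradiated lesion need not be measurable, yet local control scores it as a RECIST target lesion; patients whose lesion cannot be read that way are dropped by one rule and counted as failures by another

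*Protocol*

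**What the plan says.** **Choice of the irradiated lesion (Protocol 2.3).** Symptoms come first: "If symptoms such as pain or paralysis are present, the lesion thought to be the main cause of symptoms should be selected". Without symptoms, the largest lesion is taken, or the second largest if the largest is difficult to irradiate. The one condition on the lesion itself is size: "Tumors larger than 2 cm should be selected". The reason given is biological response, not measurability. On expected sites, the section says "the main target lesions were assumed to be liver metastases, lymph node metastases, local (surgical) recurrent lesions and bone metastases".

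**Entry (Protocol 3.1 and 3.2).** Inclusion criterion 2 asks for "Patients with more than one measurable lesion and with at least one lesion" of 2 cm or more under RECIST 1.1. That is a condition on the patient. The related exclusion is "Patients with no tumor lesions that can be irradiated", which concerns whether a lesion can be irradiated, not whether it can be measured.

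**Scoring (Protocol 2.6, local control rate).** "For evaluation, target lesions are tumors that are treated with local radiotherapy". Response is CR, PR, SD or PD by RECIST 1.1 on CT, MRI or PET-CT. A patient who does not reach CR or PR and has no progression at the sixth nivolumab dose and Day 120 is classed as SD. The closing sentence leaves lesions that cannot be evaluated out of the best-response analysis.

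**Analysis.** Protocol 2.10 works in the FAS but defines the rate as patients with CR, PR or SD over eligible patients, with a 90% Clopper-Pearson interval. SAP 6.2.2 repeats the interval, does not restate the denominator or the exclusion, and adds: "Construct a waterfall plot for the local control rate". SAP 6.7 repeats the analysis by irradiation site, SAP 8.7 lists tumor diameters over time, and SAP 6.5 plans no sensitivity analysis for missing values.

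**The concern.** The plan selects the irradiated lesion by one set of criteria and scores it by another. Selection asks whether the lesion causes symptoms or is large. Scoring assumes that it qualifies as a RECIST target lesion with a diameter to follow. Nothing joins the two, and no reading rule is given for an irradiated lesion that is not measurable. A bone metastasis chosen because it is painful is the obvious example, and the protocol expects such cases.

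A patient in this position has two possible fates in the text: absent from the analysis under Protocol 2.6, or a non-success under the formula in Protocol 2.10. The SAP does not choose between them.

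The loss would not be random. It would follow irradiation site and symptoms, and site is a planned subgroup. Protocol 1.1 also says the trial is to supply a local control percentage for planning later randomized trials. A rate that depends on an unstated choice is a weak planning figure.

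**Working it through.** The documents give no expected local control rate and no share of non-measurable irradiated lesions, so there is no figure of the plan's own to reproduce here. The 39 cases in Protocol 2.8 are sized for the primary endpoint and do not bear on this point.

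**Step 1: is measurability guaranteed?**
- Protocol 2.3 requires that the irradiated lesion cause symptoms or be the largest (or second largest), and exceed 2 cm.
- Protocol 3.1 requires that the patient have more than one measurable lesion.
- Protocol 3.2 requires that some lesion can be irradiated.

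A patient with two measurable nodes and a painful, non-measurable bone lesion above 2 cm satisfies all three, and the bone lesion is the one irradiated. Measurability is therefore not guaranteed.

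**Step 2: what happens to the rate?** Let p be the control rate among scorable lesions, f the share not scorable, and q the true control rate among those.
- Dropped (Protocol 2.6): p
- Kept as non-success (Protocol 2.10): p × (1 − f)
- All lesions read: p × (1 − f) + q × f

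Assumed inputs, not from the documents: p = 0.85 and f = 0.1, 0.2, 0.3. The last column lets q run from 0 to 1; with q = 0.85 it equals 85% in every row.

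| f | Dropped | Kept as non-success | Gap (0.85 × f) | All read, q from 0 to 1 |
|---|---|---|---|---|
| 10% | 85.0% | 0.85 × 0.9 = 76.5% | 8.5 points | 76.5% to 86.5% |
| 20% | 85.0% | 0.85 × 0.8 = 68.0% | 17.0 points | 68.0% to 88.0% |
| 30% | 85.0% | 0.85 × 0.7 = 59.5% | 25.5 points | 59.5% to 89.5% |

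Dropping returns the true rate only if q equals p, which the documents give no means of knowing.

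**Step 3: the same in whole patients.** Assumed: 40 eligible patients, about 80% control among scorable lesions, k patients not scorable. Intervals are 90% Clopper-Pearson.

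| k | Dropped | Kept as non-success | All k read as controlled |
|---|---|---|---|
| 4 | 29/36 = 80.6% (66.6 to 90.5) | 29/40 = 72.5% (58.6 to 83.7) | 33/40 = 82.5% (69.6 to 91.5) |
| 8 | 26/32 = 81.3% (66.3 to 91.5) | 26/40 = 65.0% (50.8 to 77.4) | 34/40 = 85.0% (72.5 to 93.3) |
| 12 | 22/28 = 78.6% (62.0 to 90.2) | 22/40 = 55.0% (40.9 to 68.5) | 34/40 = 85.0% (72.5 to 93.3) |

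The two rules differ by about 8, 16 and 24 points.

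**Step 4: the site subgroup.** If no lesion in a subgroup of n patients is scorable, Protocol 2.6 gives 0/0 (no estimate) and Protocol 2.10 gives 0/n = 0%.

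**Step 5: the primary endpoint.** It uses non-irradiated target lesions. If the irradiated lesion is non-measurable, the patient's measurable lesions, of which entry requires more than one, are not the ones irradiated. The primary endpoint loses nothing by this route.

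**The case against.** The strongest reply is that the protocol already has a route to SD that names no diameter. A patient short of CR or PR without progression at the sixth dose and Day 120 is SD. Protocol 2.7 has progression judged on imaging and clinical findings together, and MRI and PET-CT are allowed. On that reading, a non-progressing bone lesion counts as controlled, much as the proposed remedy would have it. This stands in part: the rule could be read to cover some of these lesions. But it sits inside a definition that invokes RECIST 1.1 and calls the lesion a target lesion, and the plan does not say that it extends to non-measurable ones.

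It is also fair that the 2 cm condition, and the choice of the largest lesion in asymptomatic patients, make measurability likely for many. That limits the number affected but guarantees nothing for lesions chosen by symptoms.

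A reader might infer three stronger things that the documents do not support:
- That painful bone metastases as a class cannot be scored. The documents cite RECIST 1.1 without reproducing it and nowhere call bone lesions non-measurable; a bone lesion above 2 cm on CT or MRI may be readable.
- That a bone subgroup would show a rate near 0% by construction. Step 4 shows that this needs every lesion in it to be unscorable and the Protocol 2.10 denominator to apply.
- That local recurrences suffer in the same way. They are listed as an expected site, but nothing suggests that they are generally non-measurable.

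**Conclusion.** The point holds as a gap in definition. The plan allows a non-measurable lesion to be irradiated, scores every irradiated lesion as a RECIST target lesion, and gives two incompatible treatments of a lesion that cannot be scored that way. The supported wording is that some irradiated lesions may not be scorable.

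Its size is unknown, because the share of such lesions is not stated. Under the assumed 85% control and 10% to 30% not scorable, the reported rate is 85% by one rule and between 76.5% and 59.5% by the other. Those lower figures belong to the Protocol 2.10 branch alone and should not be taken as the bias to expect. If the SD rule is meant to cover non-measurable lesions, the gap shrinks or closes, but the plan would have to say so.

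Local control is a secondary endpoint reported with an interval and no test, and the primary endpoint is untouched by this route. The point should be settled before the data are fixed, but it does not threaten the trial's main conclusion.

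**What to change.** Amend Protocol 2.6 (local control rate), Protocol 2.10 and SAP 6.2.2 together:

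- Score non-measurable irradiated lesions with the RECIST 1.1 non-target categories (CR, non-CR/non-PD, PD), and count CR and non-CR/non-PD as local control.
- State one denominator, keep these patients in it, and bring the closing sentence of the 2.6 definition into line with it.
- Limit the waterfall plot to measurable irradiated lesions.
- Report the rate separately for measurable and non-measurable irradiated lesions, with the number not evaluable by irradiation site. The site analysis in SAP 6.7 should follow the same rules.

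The cost is wording and a reading instruction. The scans are already scheduled, and neither lesion selection nor treatment changes. The small downside is that non-target reading is more subjective, which is why the two groups should be shown separately.
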